10.1 Primary study parameter(s)

The number of subjects enrolled, completed, or withdrawn will be summarized. Reasons for withdrawal, when known, will be provided. Demographic data will be summarized by descriptive statistics and will include total number of observations (n), mean, standard deviation (SD) and range for continuous variables, and number and percentages for dichotomous variables. The primary safety, and reactogenicity outcomes will include all subjects who meet the eligibility criteria, received the study product R0.6C, and for whom safety data are available.

Safety endpoints

For the safety analysis, data from all subjects who received at least one dose of R0.6C and for whom safety data are available will be included. All analyses will be descriptive. Data will be presented by dose, overall/dose and overall/subject. Results will be summarized by study group. The percentage of subjects with at least one local AE (solicited or unsolicited), with at least one general AE (solicited or unsolicited) and with any AE during the solicited follow-up period will be tabulated with exact 95% CI (two-sided). No multiplicity adjustment will be implemented in analysis. The same calculations will be performed for AEs rated as grade 3.

The percentage of subjects reporting each individual solicited local and general AE during the solicited follow-up period will be tabulated with exact 95% CI. The same tabulation will be performed for grade 3 AEs and for AEs with relationship to R0.6C administration. The reports of unsolicited AEs will be reviewed by a physician and will be categorized by ICD-10. The percentage of subjects with at least one report of unsolicited AE and reported up to 28 days after R0.6C administration will be tabulated with exact 95% CI. The same tabulation will be performed for grade 3 unsolicited AEs and for unsolicited AEs with a relationship to R0.6C administration. SAEs will be described in detail. Withdrawals due to AEs/SAEs will also be summarized. Vital signs which are outside of the normal range and clinically significant will also be listed in tables. The frequency of signs and symptoms will be compared between groups with the chi-square test or fishers exact test. Serious adverse events (SAEs) occurring at any point during the trial will be summarized and relatedness to vaccine will be assessed.

Any clinically important deviations in routine laboratory test results and/or vital signs as determined by the investigator will be listed. Isolated laboratory abnormalities will be reported as AEs if they are considered clinically relevant by the investigator. Vital signs which are considered clinically relevant by the investigator will be summarized. All adverse events will be listed by participant and will include details of onset time, duration, severity and relationship to the study product.

Efficacy endpoints

SMFA will be performed to determine TRA of R0.6C. Differences will be assessed by comparing mean values between time points using either a two-tailed student's t-test or a non-parametric equivalent. Paired tests will be used if pre-intervention values are compared with post-intervention values. For discrete variables (e.g. the number of positive assays), the chi-squared test or Fisher's exact test will be used (two-tailed).

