10. STATISTICAL ANALYSIS

All data will be collected and verified prior to analysis. All data will be analysed in accordance with the Statistical Analysis Plan. Final analyses of all data will occur after study completion and final verification of data according to GCP. All data analyses will be conducted using IBM SPSS, R, SAS or Graphpad using the latest version available. Detailed statistical procedures, listings, table shells, and figures will be provided in a SAP prior to analysis. The SAP will be finalized before study close-out and database lock. The following key statistical components will be considered and a detailed description will be documented in the SAP:

- Primary and secondary endpoints and how they will be measured
- Statistical methods and tests that will be used to analyze the endpoints
- Strategy that will be used if the statistical test assumptions are not satisfied
- Indication of whether the comparisons will be using one-tailed or two-tailed *t*-test (with justification of the choice) and the level of significance to be used
- Identification of whether any adjustments to the significance level or the overall P-value will be made to account for any planned or unplanned subgroup analyses or multiple testing
- Specification of potential adjusted analyses and a statement with which covariates or factors will be included
- Planned exploratory analyses and justification of their importance
- Any subgroup effects with biological justification and support from within and outside the study

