## Statistical Principles

### Confidence intervals and P values

Two-sided p values less than 0.05 will be considered statistically significant. Adjustments for multiple comparisons will be implemented where appropriate.

Where applicable, normally distributed continuous outcomes will be presented as mean with 95% CI or standard deviations. Continuous outcomes that are not normally distributed will be transformed using a suitable transformation before reporting 95% CIs or will be presented with median and interquartile ranges. For discrete (or count) data we will find interquartile ranges. Binary data will be presented as counts and proportions.

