## Analyses in relation to endpoints

### Safety outcome analyses

- For each solicited (local or general) adverse event type, possibly, probably or definitely related to the R0.6C vaccinations, the number and proportion of subjects experiencing that AE within the protocol-defined timeframe will be tabulated by severity grade for each dose/adjuvant group and for the entire study population. This will also be tabulated for subjects experiencing any solicited local, any solicited general and any solicited AE (see example table below). Where applicable, we will compare these proportions between groups. Relatedness (possibly, probably or definitely) and duration of solicited AEs to R0.6C vaccinations may also be presented. (Endpoints 1 and 3).
- For each unsolicited adverse event type (categorized by ICD-10) that is possibly, probably or definitely related to the R0.6C vaccinations, the number of adverse events per dose group and overall study population will be described categorized by severity grade. Translation from ICD-10 coding to MedDRA terms may be performed where necessary. (Endpoints 1 and 3).
- The proportion of individuals with grade 1, 2 and 3 adverse events may be compared between groups.
- The total number of grade 1, 2 and 3 adverse events as count data may be compared between groups.
- Individual serious adverse events (SAEs) will be summarized, including relatedness to R0.6C vaccinations (Endpoint 1).
- Withdrawals due to AEs/SAEs will be summarized per group.

Table 1 - Descriptive statistics for subjects experiencing solicited AEs

		30µg R0.6C/AI OH		30µg R0.6C/AI OH + Matrix-M		100µg R0.6C/AI OH		100µg R0.6C/AI OH + Matrix-M		All	
		#Subjects	%	#Subjects	%	#Subjects	%	#Subjects	%	#Subjects	%
Local AE1	Grade 1										
	Grade 2										
	Grade 3										
	Any grade										
Local AE2	Grade 1										
	Grade 2										

	...										
	....										
Any local AE*	Grade 1										
	Grade 2										
	Grade 3										
	Any grade										
Systemic AE1	Grade 1										
	Grade 2										
	...										
Any systemic AE*	Grade 1										
	Grade 2										
	...										
Any AE*	Grade 1										
	Grade 2										
	...										

\* List (only) highest grade AE per subject

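### Safety comparisons between groups are called descriptive and unadjusted yet are to be tested, the SAP does not settle the rule, and no interval for a between-group difference is planned

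*Protocol*

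**What the plan says.** **Protocol section 10.1, safety endpoints.** "All analyses will be descriptive". Percentages of subjects with events are tabulated with exact 95% confidence intervals, and "No multiplicity adjustment will be implemented in analysis". Later in the same text: "The frequency of signs and symptoms will be compared between groups with the chi-square test or fishers exact test". No rule is given for choosing between the two tests, and the groups or pairs to be compared are not named.

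**Protocol section 10.** Data are to be analysed according to the SAP. Among the items the SAP must document is: "Identification of whether any adjustments to the significance level or the overall P-value will be made".

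**SAP, Confidence intervals and P values.** "Two-sided p values less than 0.05 will be considered statistically significant". Then: "Adjustments for multiple comparisons will be implemented where appropriate". No method, no family of comparisons and no statement about safety follows.

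**SAP, Safety outcome analyses.** For solicited events: "Where applicable, we will compare these proportions between groups". For graded events: "The proportion of individuals with grade 1, 2 and 3 adverse events may be compared between groups". No test is named and adjustment is not mentioned.

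**Protocol section 8.2.** Adjuvant (arm A or B) is randomised within each group. Subjects may choose their dose group.

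**The concern.** A compulsory chi-square or Fisher test is not a descriptive analysis, so section 10.1 disagrees with itself. The protocol hands the multiplicity decision to the SAP, and the SAP does not make it for safety. Four things stay open: whether a test is run, which test, at what level, and over which family. In an open-label trial these could be settled with group results already in view.

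The larger loss is in what gets reported. The only planned safety intervals are for percentages within a single group; neither document plans one for a difference between groups. Whether Matrix-M adds reactogenicity is the one safety contrast protected by randomisation. Under the plan as written it could be reported only as a list of symptom-level p-values from very small groups.

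**Working it through.** **Inputs.** Eight subjects in each of four dose-adjuvant groups (Protocol 5.4), so 16 v 16 when one adjuvant is compared with the other over both doses. Solicited symptoms: 6 systemic and 5 local, 11 in all (Protocol 9.2.2). Significance level 0.05, two-sided (SAP). No stated figure is in dispute. The SAP's one safety sample-size figure reproduces: 1 - (1 - 0.07)^32 = 90.2%.

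**Step 1: how much turns on the open adjustment rule.** Take every 8 v 8 table with more events in one group than the other, counting mirror images once. Ten have two-sided Fisher p<0.05:

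| Events out of 8 v 8 | Fisher p |
|---|---|
| 8 v 0 | 0.00016 |
| 7 v 0, 8 v 1 | 0.0014 |
| 6 v 0, 8 v 2 | 0.0070 |
| 7 v 1 | 0.0101 |
| 5 v 0, 8 v 3 | 0.0256 |
| 6 v 1, 7 v 2 | 0.0406 |

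Neither document names a method or family, so Bonferroni (0.05/k) and k are assumptions, shown over a range:

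| k | Possible origin | Threshold | Patterns remaining |
|---|---|---|---|
| 4 | illustrative | 0.0125 | 6 |
| 6 | all pairs of four groups, one symptom | 0.0083 | 5 |
| 11 | one test per solicited symptom | 0.0045 | 3 |
| 66 | 11 symptoms x 6 pairs | 0.00076 | 1 |

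For example, 7/8 v 2/8 (p=0.0406) passes unadjusted and fails at every k shown.

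**Step 2: the open choice of test.** Five further 8 v 8 patterns are below 0.05 by uncorrected chi-square but not by Fisher. Two of them are 4 v 0 (0.021 v 0.077) and 5 v 1 (0.039 v 0.119).

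**Step 3: power.** Power is the sum, over all tables with Fisher p<0.05, of the product of the two binomial probabilities. The rates are illustrative assumptions.

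| True rates | 8 v 8 | 16 v 16 |
|---|---|---|
| 20% v 60% | 24% | 50% |
| 10% v 40% | 10% | 36% |

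**Step 4: what an interval shows that a p-value hides.** The Newcombe limits for d = p1 - p2, with Wilson limits (l, u) for each proportion, are d - sqrt[(p1 - l1)² + (u2 - p2)²] and d + sqrt[(u1 - p1)² + (p2 - l2)²].

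- 5/8 v 2/8: d = 0.375, Wilson limits 0.306 to 0.863 and 0.071 to 0.591. Lower: 0.375 - sqrt(0.319² + 0.341²) = -0.09. Upper: 0.375 + sqrt(0.238² + 0.179²) = 0.67. Fisher p=0.31.
- 10/16 v 4/16, the same proportions over both doses: Wilson limits 0.386 to 0.815 and 0.102 to 0.495. Lower: 0.375 - sqrt(0.239² + 0.245²) = 0.03. Upper: 0.375 + sqrt(0.190² + 0.148²) = 0.62. Fisher p=0.073.

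The 8 v 8 result would be reported as not significant, yet it is compatible with an excess of up to 67 percentage points. Combining the doses narrows the interval from about 76 points to about 58. In the second case the Newcombe interval excludes zero while Fisher p exceeds 0.05, so one interval method should be fixed in advance and not used as a disguised test.

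**The case against.** **The two documents can be read together.** The SAP's multiplicity sentence is a trial-wide principle. Beside the protocol's safety text it can mean that adjustment is not appropriate for safety. A reader might infer that the documents give flatly opposite instructions, so that one table is both significant and not significant. The text does not support that: the SAP nowhere says safety p-values are adjusted. What stands is that it does not say they are exempt either, although the protocol gave it that decision. The no-adjustment sentence sits beside the interval tabulations; if it covers only those, the tests have no multiplicity rule at all.

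**The SAP softens the tests.** It makes comparisons conditional or optional, and comparing proportions need not mean testing them. This is correct, and it leaves open whether the protocol's compulsory test is run.

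**The family is assumed.** Sixty-six tests with Bonferroni is the harshest reading, and one four-group test per symptom is equally consistent with section 10.1. This is accepted, hence the range.

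**Low power is disclosed.** Protocol 5.4 and the SAP's sample size section both say comparisons can detect only very large differences, and both call the study largely descriptive. Neither says a non-significant result will be read as similar tolerability; that is a risk of misreading, not a stated plan. The admission itself argues for estimates over tests.

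**No decision depends on it.** The primary safety endpoint is a count of serious and related grade 3 events. The holding rules and group progression use no p-values. No listed objective or endpoint is a between-group safety comparison. All of this stands and limits the severity.

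**Conclusion.** The point holds as a minor one. Section 10.1 is internally inconsistent, and the SAP leaves unresolved whether its significance and multiplicity sentences apply to safety. The consequence is confined to how reactogenicity differences between groups are interpreted. Depending on the adjustment assumed, between 4 and 9 of the ten nominally significant 8 v 8 patterns would lose that label (10 - 6 and 10 - 1). These counts rest on Bonferroni with 4 to 66 tests, and the power figures rest on the illustrative event rates. The firmer conclusion needs neither assumption about adjustment: in groups of 8, a symptom-level p-value says little, and failure to reach 0.05 is not evidence of similar tolerability. A difference with its interval, combined over doses for the randomised adjuvant contrast, would say more from the same data. Sample size, holding rules, group progression and the primary endpoints do not change.

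**What to change.** Keep the protocol's descriptive rule and bring the other sentences into line with it before database lock.

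1. In Protocol 10.1 and the SAP's safety section, make the main between-group summary the difference in the proportion of subjects with the event, Alhydrogel + Matrix-M minus Alhydrogel, with a 95% CI. Name one method (Newcombe or exact). Give it at each dose (8 v 8) and over both doses (16 v 16).
2. Give any 30 v 100 µg contrast in the same form, labelled non-randomised because subjects may choose their dose group.
3. If p-values are kept, use Fisher's exact test, label them nominal and unadjusted, make no claim of significance, and state that p>0.05 is not evidence of equal safety.
4. In the SAP's section on confidence intervals and p values, state that the significance threshold and the multiplicity sentence do not apply to safety.

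The cost is wording in two documents and one extra table. The trial gives up symptom-level significance claims.

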5.4 Sample size justification

R0.6C is a phase 1 safety and efficacy trial in healthy volunteers, designed to identify safety concerns associated with R0.6C administration at different dosages and/or adjuvants. A total of 32 healthy adults (males and females) aged 18 – 55 will be divided over four groups. Each group will include eight subjects.

Sample size for each group is appropriate based on similar trial designs in malaria protein vaccination studies. This is a small Phase 1 study; therefore, it is largely descriptive and is intended to provide primarily safety data of 2 doses of R0.6C combined with 2 adjuvants. Comparative statistics will be performed but will have low power to detect anything other than very large differences between the groups.

Furthermore, if we assume an effect size of 75% TRA at 14 days after the fourth R0.6C vaccination (I4+I4) compared to baseline (I1-I1), with the subject size of n=8 per dose/adjuvant arm we will have an empirical power of >99%, based on calculations and assumptions as described below in paragraph 5.4.1.

5.4.1 Estimation of empirical power for an analysis of transmission reducing activity under different assumptions

The simulation algorithm

1. We generate n_0 subjects in the control (pre-treatment) group and n_1 subjects in the treatment (post-treatment) group with a variable x_i to indicate whether the subject is in the control group ($x_i = 0$) or in the treatment group ($x_i = 1$).
2. We generate m mosquito dissections for each subject.

3. We simulate subject-specific random intercepts (z_i) from a normal distribution with a mean of 0 and a specified standard deviation σ , i.e. $Z \sim N(0, \sigma)$.

4. Lastly we generate the oocyst counts (y_{ij}) for each subject i and mosquito j using a negative binomial distribution such that $Y \sim NB(\mu, \theta)$ where θ is the anticipated dispersion parameter and $\mu_{ij} = \exp(\beta_0 + \beta_1 x_{ij} + z_i)$ where β_0 is the anticipated mean of the log oocyte counts in the control group and β_1 is the anticipated regression coefficient used to estimate the TRA, such that

$$\beta_1 = \log\left(1 - \frac{TRA}{100}\right).$$

The model

To analyze the simulated data, we make the of the *mgcv* package in R. We run a Generalized Additive Mixed Model such that,

$$\log(y) = \beta_0 + \beta_1 x + z_i.$$

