### Sample size

STOP-TRANS is an exploratory first-in-human study with the objective to identify large safety and tolerability signals. In addition, SMFAs are done to provide a first proof-of-concept. The study is largely descriptive and is intended to provide primarily safety data of 2 dose levels of R0.6C combined with 1 or 2 adjuvants given 4 times over 24 weeks. Comparative statistics will be performed but will have low power to detect anything other than very large differences between the groups. In total 32 participants will receive R0.6C. Based on a binomial distribution, this means that the probability to detect at least one clinically significant event (e.g. a serious adverse reaction) during vaccination with a power of 90% is 7%.

Furthermore, if we assume an effect size of 75% TRA at 14 days after the fourth R0.6C vaccination (I4+I4) compared to baseline (I1-I1), with the subject size of  $n=8$  per dose/adjuvant arm we will have an empirical power of >99% ( $\alpha=0.05$ ) to detect this, based on calculations and assumptions as described in the next paragraph.

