### Efficacy outcome analyses

- Pfs48/45-6C and R0.6C antibody prevalence and density will be determined by ELISA; the mean of duplicate concentration estimates is used for analyses. Antibody density will be expressed in  $\mu\text{g/mL}$  using humanized monoclonal antibody TB31F as a reference/standard. (Endpoint 5, 7 and 11).
- The R0 antibody prevalence and density will be determined by ELISA; the mean of duplicate concentration estimates is used for analyses. Antibody density will be expressed in  $\mu\text{g/mL}$  using R0 monoclonal antibody as a reference/standard. Alternatively, R0 antibody densities may be expressed in arbitrary units (AU) or R0 antibody densities may be estimated by subtracting measured R0 antibody levels from R0.6C antibody levels. (Endpoint 8).
- Pfs48/45-6C antibody density will be plotted over time per individual and either as a mean or geometric mean per group. AUC and mixed effects models may be used to investigate the effect of timepoints, dose/adjuvant group and their interactions on the 6C antibody concentration. Mixed models use specific random intercepts to control for the correlation within individuals (Endpoint 7).

- TRA will be quantified as the relative reduction in oocyst intensity for test samples (one feeder per test sample) compared to baseline serum controls. Samples may be tested in one or two independent SMFA experiments. If significant transmission reduction is measured, TRA values for each participant and time-point will be estimated using generalized linear models, as previously described. (Endpoint 2, 4 and 10).
- We may calculate the percentage of individuals per group that have at least 50%, 80% and 90% TRA at relevant timepoints and the percentage of individuals per group with statistically significant TRA at relevant timepoints. Mean TRA levels may also be calculated per study group per time point and compared between groups. (Endpoint 10).
- Modeled TRA estimates (based on antibody concentration) may be plotted against observed TRA estimates.
- TBA will be quantified as the reduction in oocyst prevalence in the presence of test serum as compared to (pooled) baseline serum^1 and presented per group and time-point. (Endpoint 6).

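### The primary TRA test in Protocol 10.1 has no stated scale and is not the log-link count model behind the power claim of over 99%, and the SAP does not settle which test decides significance

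*Protocol*

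**What the plan says.** Protocol 10.1, Efficacy endpoints, gives the test for SMFA results: "Differences will be assessed by comparing mean values between time points using either a two-tailed student's t-test or a non-parametric equivalent". It adds: "Paired tests will be used if pre-intervention values are compared with post-intervention values". It does not say whether the values averaged are oocyst counts, log counts or TRA percentages, nor how to choose between the t-test and its rank alternative.

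The power claim in Protocol 5.4 starts from an assumed effect ("if we assume an effect size of 75% TRA at 14 days after the fourth R0.6C vaccination") and concludes "with the subject size of n=8 per dose/adjuvant arm we will have an empirical power of >99" per cent. The SAP repeats it under Sample size. Both documents derive the figure from negative binomial oocyst counts with a log link and subject random intercepts, testing beta1 = log(1 - TRA/100). The simulation generates "subjects in the control (pre-treatment) group and" a separate set of post-treatment subjects.

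Protocol 10 defers to the SAP. Under Efficacy outcome analyses the SAP says: "TRA will be quantified as the relative reduction in oocyst intensity for test samples (one feeder per test sample) compared to baseline serum controls". It then brings in generalized linear models for each participant and time point, but only once a significant reduction has been found. Under Statistical Software it sends SMFA data to an online tool without stating the tool's model or hypothesis test. The significance level is general: "Two-sided p values less than 0.05 will be considered statistically significant".

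**The concern.** The test named for the primary endpoint is not the analysis that was powered, and the SAP neither repeats nor withdraws it. TRA is a ratio. With a between-subject SD of 0.64 on the log scale, raw oocyst means are right-skewed, and a t-test on them gives most weight to the few sera with high counts.

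More than presentation depends on the answer. Note 8 to the schedule in Protocol 8.3.17 allows SMFA at the other time points to be dropped if I3+14 and I4+14 show no significant reduction. The SAP makes its TRA modelling and its PK-PD modelling depend on significance too. A weaker or undefined test could therefore cost a moderately effective group its secondary TRA data.

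**Working it through.** **Inputs.** From Protocol 5.4.1 and the SAP's Simulation results: beta0 = 3.7037, theta = 4.451, sigma = 0.64, m = 20 mosquitoes. Group size is 8 and alpha is 0.05 two-sided. TRA 75% gives beta1 = ln 0.25 = -1.386. The pre/post correlation rho of the subject intercepts is not in the documents, so 0, 0.5, 0.8 and 1 are assumed.

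**Step 1: reproduce the plan's figure.** On the log scale, the variance per serum is v = sigma^2 + (1/mu + 1/theta)/m.
- Baseline: mu = exp(3.7037) = 40.6, so v0 = 0.4096 + (0.0246 + 0.2247)/20 = 0.4221.
- Post: mu = 10.15, so v1 = 0.4096 + (0.0985 + 0.2247)/20 = 0.4258.
- 10 baseline v 8 post subjects: SE = sqrt(0.4221/10 + 0.4258/8) = 0.3089; 1.386/0.3089 = 4.49; power = Phi(4.49 - 1.96) = 99.4%. The plan's table gives 99.8%. Fitting the count model by maximum likelihood to 300 simulated data sets gives 99.3%.
- The same check at TRA 50%: plan 63.8%, formula 61.3%, fitted model 66.7%.

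The stated figure is therefore reproduced, and it belongs to the log-scale model. The tables start at 10 baseline subjects. For 8 v 8, SE = 0.3255, the ratio is 4.26 and power is 98.9% (97.3% from 300 fitted simulations).

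**Step 2: a paired test on the log scale.** For d = ln(post mean) - ln(baseline mean), Var(d) = v0 + v1 - 2 x rho x sigma^2. At rho 0, 0.5, 0.8 and 1 this is 0.848, 0.438, 0.192 and 0.029. The noncentrality 1.386/sqrt(Var(d)/8) is 4.26, 5.92, 8.94 and 23.2. On 7 df that gives power of 95.2%, 99.9% and, for the last two, over 99.9%, in agreement with the simulation below.

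**Step 3: simulate the candidate tests.** The plan's data generator was used with 8 pairs and 20,000 groups per scenario. Entries are power in %.

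| Test | TRA | rho 0 | rho 0.5 | rho 0.8 | rho 1 |
|---|---|---|---|---|---|
| Paired t, raw feeder means | 75% | 84.7 | 94.2 | 97.1 | 98.5 |
| Wilcoxon, raw differences | 75% | 90.6 | 99.1 | 100 | 100 |
| One-sample t on subject TRA | 75% | 87.0 | 98.9 | 100 | 100 |
| Paired t, log means | 75% | 95.3 | 99.9 | 100 | 100 |
| Paired t, raw feeder means | 50% | 35.7 | 56.5 | 83.9 | 97.9 |
| Wilcoxon, raw differences | 50% | 37.6 | 61.8 | 91.4 | 100 |
| One-sample t on subject TRA | 50% | 35.1 | 62.5 | 94.1 | 100 |
| Paired t, log means | 50% | 45.4 | 72.2 | 96.8 | 100 |

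With no effect, the raw paired t-test rejects 3.6 to 4.1% of the time and the log version 4.9 to 5.2%.

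**Step 4: isolate the effect of scale.** Log t minus raw t on the same 8 pairs is 10.6, 5.7, 2.9 and 1.5 points at TRA 75%, and 9.7, 15.7, 12.9 and 2.1 points at TRA 50%.

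**Step 5: what each test estimates.** Under the plan's model, a zero difference in mean counts is the same hypothesis as a ratio of 1, that is, TRA = 0. The raw test's interval, however, is for a difference in oocysts. Only the log-scale analysis gives an interval that back-transforms to TRA = 1 - exp(estimate).

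**The case against.** The strongest reply is that the SAP governs, defines TRA as a ratio, names generalized linear models and a dedicated tool, and allows non-normal outcomes to be transformed before intervals are reported. That answers part of the estimation question. It does not supply the group-level test: the models come after significance, no hypothesis test is given for the tool, and the transformation rule concerns reporting.

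A reader might infer more than the documents support.
- **That the plan commits to raw oocyst means.** It does not; raw means are one reading. Subject-level TRA is another, and it is workable as a one-sample test against zero.
- **That every permitted test falls short of 99%.** At TRA 75%, the rank test reaches about 99% or more once rho is 0.5 or higher.
- **That a raw-scale t-test does not test TRA.** It does test TRA = 0; it lacks the estimate and interval.
- **That the whole gap between the raw t-test and 99% is due to scale.** The 99% was tabulated only for 10 or more baseline subjects in an unpaired layout. Even the log-scale paired t-test reaches only 95.3% at rho = 0.

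It is also fair that both documents call the study largely descriptive. And a log-mean t-test can mislead when sera block completely. As an assumed example, take a baseline of 812 oocysts per feeder, two of eight sera fully blocking and six inert. With a half-oocyst offset, mean d = 2 x ln(0.5/812.5)/8 = -1.85, so the reported TRA is 84% (p = 0.17), although mean oocysts fell by only 25%. That test should not stand alone.

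**Conclusion.** The point holds as a mismatch and an unresolved choice. The only group-level test named for the primary comparison has no stated scale and is not the analysis behind the power figure, and the SAP leaves the deciding test unnamed. If raw feeder means are used, the paired t-test has about 85 to 98% power at TRA 75%, below the stated figure at every correlation tried. At TRA 50% it loses about 10 to 16 points to a log-scale paired test for rho up to 0.8, and about 2 points at rho = 1.

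At TRA 75% the practical loss is small if rho is high or the rank test is chosen. These sizes rest on the plan's own inputs, complete data on 8 pairs, and an assumed range for rho. Because significance controls later assays and modelling, the gap is more than missing detail, and it should be closed before analysis.

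**What to change.** In Protocol 10.1 and SAP Efficacy outcome analyses, name one primary analysis for the SAP's Endpoints 2 and 4: a negative binomial mixed model with log link, with a subject effect linking I1-1 to the post-vaccination sample, reporting TRA = 1 - exp(beta1) with a 95% CI for each dose-adjuvant group. The subject effect should let the response vary between subjects, because a shared intercept alone amounts to assuming rho = 1.

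Use the paired t-test on ln(post/pre) as a small-sample check, with a sensitivity analysis on the offset for feeders with no oocysts. Make the primary analysis the significance criterion in note 8 of Protocol 8.3.17, in SAP Statistical Software, and in the conditional modelling step of SAP Efficacy outcome analyses.

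Replace the claim of over 99% with power for 8 pairs over a stated correlation range. For the log-scale paired t-test this is about 95% to over 99% at TRA 75%, and about 45% to 100% at TRA 50%.

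The cost is wording and a little more analysis work, a decision on zero-oocyst feeders, and a slightly less favourable power figure. No extra subjects, samples or assays are needed.
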